7. PLANNED ANALYSIS

For End-Of-Text (EoT) tables, the set of summary statistics is: N / Mean / SD / SE / Min / Q1 (lower quartile)/ Median / Q3 (upper quartile)/ Max. The 1st and 99th percentiles might be substituting minimum and maximum in tables with open-ended values to safeguard against implausible extremes.

Geometric means and ranges will be added to the presentation or replace the presentation of mean and standard deviation for parameters which rather follow a log-normal distribution than a normal distribution.

Statistical parameters will be displayed to a defined number of decimal places as specified in the BI guideline “Reporting of Clinical Trials and Project Summaries” [\(4\)](#)

Tabulations of frequencies for categorical data will include all possible categories and will display the number of observations in a category as well as the percentage (%) relative to the respective treatment group (unless otherwise specified, all patients in the respective patient set whether they have non-missing values or not). Percentages will be rounded to one decimal place. The category missing will be displayed only if there are actually missing values.

Disposition of the patient population participating in the trial will be analysed by treatment groups and presented in the clinical trial report as a frequency-distribution.

Disposition as required for reporting for the trial in EudraCT will be provided. Enrolment will be summarised by country and by age group for reporting in EudraCT. (see [\(13\)](#)).

Number of patients lost to follow up (no information on vital status after start of study closure) and number of patients lost to follow up for the primary endpoint (no information on primary endpoint after start of study closure) will be summarised.

The reason for not randomising screened patients will be summarized descriptively.

The frequency of patients with IPDs will be presented by treatment group for the randomised set. The frequency of patients in different analysis sets will also be analyzed for each treatment group.

Descriptive statistics on impact of COVID-19 on study visits as well as study medication intake will be provided.

7.1 DEMOGRAPHIC AND OTHER BASELINE CHARACTERISTICS

Demographics and baseline characteristics will be analyzed based on RS. Demographics will be repeated on the TS if the analysis sets differ by more than 1%. Standard descriptive analysis and summary tables will be presented. These summary tables will include description of subgroup variables detailed in [Section 6.4](#). Descriptive analysis of the following variables measured at baseline will be presented: Age, body mass index (BMI), time since diagnosis, systolic blood pressure (SBP), diastolic blood pressure (DBP), heart rate, weight, eGFR, UACR, NT-pro BNP, LVEF, hemoglobin and troponin T. HbA_{1c} will be presented for patients with diabetes at baseline. NTproBNP will be shown for patients with or without atrial fibrillation/ atrial flutter at baseline.

A summary of the number of patients in each randomisation stratum per treatment will also be shown. The information will be based upon the data received from the interactive voice response system (IVRS) provider. Analyses will be based on actual information collected via the CRF / central laboratory, not via IVRS.

7.2 CONCOMITANT DISEASES AND MEDICATION

Only descriptive statistics are planned for this section of the report using the randomised set. Concomitant medication use will be summarised by Anatomical-Therapeutic-Chemical classification level 3 (ATC3) and preferred name. Summaries will be presented for concomitant therapies taken at baseline and separately those taken after baseline. Separate summaries of use of heart failure-related drugs (e.g. ARNi, beta-blockers, ivabradine, diuretics, ACE-inhibitors, ARBs, MRAs, cardiac glycosides), anticoagulants, acetylsalicylic acid (ASA), or lipid lowering drugs at baseline and newly introduced after baseline will be presented. Use of devices and other non-medication therapy at baseline and newly introduced after baseline will also be summarized. Changes of diuretic therapy over time will be summarized.

Concomitant diseases will be summarised by system organ class and preferred term. Relevant medical history by treatment group will also be presented. Both summaries will be presented using the randomised set.

7.3 TREATMENT COMPLIANCE

Only descriptive statistics are planned for this section of the report. The number and percentage of patients with overall compliance will be reported. Overall compliance will be calculated as a weighted average of reported compliance. The sum of all reported compliance over the planned visits will be divided by the total duration. The treated set of patients will be considered.

7.4 PRIMARY ENDPOINT

The primary estimand of this trial is the hazard ratio of the time to first event of adjudicated HHF or adjudicated CV death between empagliflozin 10 mg and placebo in the population of patients with heart failure with preserved ejection fraction. The primary comparison will be made regardless of changes of treatment (including discontinuation of trial medication) until completion of the planned treatment phase. For clarification, this excludes events and time at risk after the protocol-specified treatment discontinuation for patients that complete the treatment period according to protocol.

7.4.1 Primary analysis of the primary endpoint(s)

As the primary endpoint, time to the first event of adjudicated HHF or adjudicated CV death will be reported in days. The primary analysis will be based on RS, using all data available until completion of the planned treatment phase, including the data after end of treatment for patients not completing the treatment phase as planned.

The primary endpoint will be displayed using cumulative incidence function (CIF) curves and expressed as the hazard ratio with associated two-sided 95% confidence intervals (CIs) and two-sided CIs based available alpha-level for the analysis.

For the interim analysis and final analysis, the following Hwang, Shih and De Cani α -spending function at information fraction t_k with parameter $\gamma = -8$ will be used:

$$\alpha^*(\gamma, t_k) = \min \left\{ \alpha, \quad \alpha \frac{1 - e^{-\gamma t_k}}{1 - e^{-\gamma}} \right\} = \min \left\{ 0.025, \quad 0.025 \frac{1 - e^{8t_k}}{1 - e^8} \right\}$$

The alpha levels are expected to be 0.001 and 0.0248 (one-sided) for the interim and final tests respectively, when the interim analysis occurs at the time of 60% information.

Estimator and corresponding confidence intervals will not be corrected for interim analysis.

The primary endpoint will be analysed using Cox regression, with factors of treatment (empagliflozin, placebo), region (North America, Latin America, Europe, Asia and “other” including India, South Africa and Australia), baseline status of diabetes (diabetes, prediabetes, no diabetes), age (continuous), sex, left ventricular ejection fraction (LVEF) (continuous) and eGFR (CKD-EPI)_{cr} at baseline (continuous). Since the stratification factors are included in the model as covariates, no stratified Cox regression will be used.

Breslow’s method will be used for dealing with ties.

The individual relevant components of the composite will be summarized descriptively. In this descriptive analysis of the relevant component for the composite, CV death after HHF will not be counted. In all other analyses of CV death alone defined in this document, all CV deaths will be counted, disregarding any earlier events.

A hierarchical testing procedure will be followed for the assessment of the primary and key secondary endpoints. For all endpoints, superiority of empagliflozin vs. placebo will be evaluated using a two-sided test.

The tests will be performed in the following hierarchical order:

1. Time to first event of adjudicated CV death or adjudicated HHF
2. Occurrence of adjudicated HHF (first and recurrent)
3. eGFR (CKD-EPI)_{cr} slope of change from baseline

Starting from step 1, if the null hypothesis of no difference is rejected, and the result is more favourable for empagliflozin, superiority is concluded in the tested endpoint, and the overall type I error is preserved for the test in the next step. If at any step the null hypothesis of no difference is not rejected, subsequent tests are conducted in an exploratory manner.

The overall type I error rate will be preserved at a level of 0.05 (2-sided). The type I error rate used at the final analysis will be influenced by the pre-planned interim analysis.

In the final analysis after the evaluation of recurrent HHF, alpha will be split into 0.001 to be used for the analysis of eGFR slope, and the rest will be transferred to the meta-analyses.

In case the trial is finished early at the time of interim analysis, using $\alpha_{interim}$ for the primary and key secondary endpoints in the testing hierarchy according to the α -spending function above, the following α -split will be used for the eGFR slope analysis and the meta-analysis:

0.1 * $\alpha_{interim}$ will be used for the eGFR slope analysis and

0.9 * $\alpha_{interim}$ will be transferred to the meta-analyses

In both the interim and final analyses, if the slope analysis is successful, the alpha of this branch will then be transferred to the meta-analyses.

The testing hierarchy is summarized in Figure 7.4.1: 1.

[figure not shown]

Figure 7.4.1: 1 Hierarchical analysis of trial in HFpEF (1245.110) and the parallel trial in HFrEF (1245.121) showing the alpha-spending at the final analysis

7.4.2 Sensitivity analyses

The following sensitivity analyses will be conducted:

- A Cox model including only treatment as covariate, not adjusting for any other variables.

- The same Cox regression as the primary analysis will be performed on the TS, with observation period up to 30 days after treatment discontinuation. Total number of patients with primary events occurring during the 30 days after treatment discontinuation will also be tabulated.
- For patients who are without primary event and lost to follow up before trial completion, the treatment specific incidence rates for empagliflozin and placebo for retrieved drop-outs will be used to impute the primary events in a multiple imputations framework. The primary model will be applied to the imputed datasets. It is planned to perform 100 imputations. Rubin's rules will be used to summarize the log hazard ratios and the result will be back-transformed to show a hazard ratio with confidence interval.
- The endpoint will be evaluated based on investigator defined events (same model as the primary primary analysis). Investigator defined HHF includes AEs ticked by the investigator as "Hospitalisation due to heart failure". Investigator defined CV death includes AEs ticked by the investigator as "CV death other than CV death attributed to myocardial infarction or stroke", "Undetermined cause of death" as well as HHF, CV hospitalization, MI or stroke if the event was fatal.
- A competing risk model by Fine-Gray will be explored, including the same set of covariates as in the primary analysis, sub-distribution hazard ratios will be provided [\(5\)](#).
- The primary analysis will be repeated to include all events up to individual trial completion including the follow-up period.
- The primary analysis will be repeated to include only confirmed primary events which meet the CDISC guidance criteria for hospitalization for heart failure (i.e., confirmed by adjudication committee, but excluding those missing a physical sign or laboratory test, or both)
- A Cox model including additional prognostic covariates, Log(NTProBNP), baseline atrial fibrillation/atrial flutter, and HHF in last 12 months, in addition to the covariates in the primary model.
- COVID-19 sensitivity analyses will be conducted:
 - The primary analysis will be repeated to include all events up to cutoff dates prior to COVID-19 outbreak – cutoff (censoring) dates are 30Nov2019 for China and 31Dec2019 for all other countries.
 - The same Cox regression model as for the primary endpoint will be fitted, however, adding an additional time dependent covariate for COVID-19 outbreak (time dependent covariate being 0 before outbreak date defined above and 1 thereafter)

- The same Cox regression model as for the primary endpoint will be fitted, however, adding an additional time dependent covariate for COVID-19 outbreak as well as a treatment by COVID-19 outbreak interaction term
- The primary analysis will be repeated to include all events up to 7 days prior a reported SARS-CoV-2 infection (based on broad scope SARS-CoV-2 infections)

A Kaplan-Meier curve of time to censoring for primary endpoint will be presented in order to assess whether there was differential censoring. For this analysis, a primary endpoint event will be counted as censoring and a censoring (including censoring due to the competing event of non-CV death) will be counted as an event.

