9.6 DETERMINATION OF SAMPLE SIZE

The trial is designed to achieve a power of 90% for a two-sided test with $\alpha=0.05$ and hazard ratio 0.80. To achieve this at least 841 patients with a primary event are required.

Including the interim analysis with Hwang, Shih and De Cani α -spending function at 60% information with parameter $\gamma = -8$ will diminish the power only slightly to 89.98%.

The drop-out rate from the trial is assumed to be very low ($< 1\%$ per year) and is not considered for determination of sample size.

A 10% yearly event rate in the placebo group is assumed. Assuming an accrual period of 18 months and a follow-up period of 20 months, it was planned to randomise 4126 patients to accrue 841 events.

The event rate and recruitment progress is assessed in a blinded manner during recruitment before any interim unblinding. If the accumulated blinded data suggests a slower accrual of

primary outcome events over calendar time than originally projected, then the number of randomised patients may be increased to a maximum of 6000 patients. Operationally, the recruitment period would be extended and could continue up to 6 months before the target number of events is expected to be achieved. The number of confirmed primary outcome events will not be affected by this consideration and will remain 841 events.

While monitoring the event rate in the above described manner, it was planned to include approximately 5750 patients in the trial.

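### The primary Cox model could gain some power at low cost by including the three baseline covariates that the SAP itself calls prognostic; this is an improvement, not an error

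*SAP*

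**What the plan says.** All references are to the revised SAP of February 2021.

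- **Primary model (7.4.1).** Cox regression with treatment, region, baseline diabetes status, age, sex, LVEF and baseline eGFR. On stratification it says: "Since the stratification factors are included in the model as covariates, no stratified Cox regression will be used".
- **Sensitivity model (7.4.2).** "A Cox model including additional prognostic covariates, Log(NTProBNP), baseline atrial fibrillation/atrial flutter, and HHF in last 12 months", fitted on top of the primary covariates. No reason is given for the ranking of the two models, and no hazard ratio, prevalence or distribution for the three variables.
- **Missing covariates (6.6.1).** For Cox models the overall median (continuous) or the most frequent category (categorical) is imputed.
- **Design (9.6).** 90% power, two-sided 0.05, "hazard ratio 0.80. To achieve this at least 841 patients with a primary event are required". With the interim analysis, this "will diminish the power only slightly to 89.98"%. The calculation takes no credit for covariate adjustment.
- **Atrial fibrillation (Table 6.4: 1, footnotes).** Two definitions are in use: fibrillation or flutter on the baseline ECG, and a history from any pre-treatment ECG or the medical history. The 7.4.2 item does not say in so many words which one it means.

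**The concern.** In a Cox model, leaving out a variable that predicts the outcome pulls the estimated hazard ratio toward 1 and weakens the test, even in a perfectly randomised trial. Here the plan has identified three such variables, uses them elsewhere (NT-proBNP, recent HHF and history of atrial fibrillation or flutter are subgroup variables in Table 6.4: 1) and already specifies a model that contains them. With 841 events, three more parameters are no burden.

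The primary test is also the gate for the hierarchy in 7.4.1: recurrent HHF, eGFR slope and the alpha passed to the meta-analyses all depend on it. A modest gain in power there, with type I error unchanged, is worth having.

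**Working it through.** **1. The plan's own figures**

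- Events (Schoenfeld): 4 × (1.960 + 1.282)² / (ln 0.80)² = 844.1, so 845. Freedman's formula gives 852. The SAP has 841.
- Power at 841 events: Φ(√841/2 × 0.2231 − 1.960) = Φ(3.236 − 1.960) = 89.9%.
- Spending function at 60% information, γ = −8: 0.025 × (1 − e^4.8)/(1 − e^8) = 0.00101; the final level is 0.02483. The SAP says "The alpha levels are expected to be 0.001 and 0.0248 (one-sided) for the interim and final tests respectively". Group-sequential power is 89.87%, against the stated 89.98%.
- Sample size: "A 10% yearly event rate in the placebo group is assumed" and "Assuming an accrual period of 18 months and a follow-up period of 20 months". Reading 10% as an annual probability, with exponential times and uniform accrual, the mean event probability over both arms is 0.2039, and 841/0.2039 = 4125. The SAP has 4126.

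The design reproduces with no contribution from the three covariates.

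**2. Cost of omission**

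Let the three covariates, after allowing for those already in the model, add a normal term with variance s² to the log hazard. Let W be the corresponding multiplier of the hazard and H(t) the mean cumulative hazard. At time t, the model without them estimates the log hazard ratio multiplied by approximately

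1 − H(t) × Var(W | event-free at t) / E(W | event-free at t).

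Averaging this factor over the event times gives r. Effective events are 841 × r².

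Inputs from the SAP: 841 events, N = 5750 or 4126, 10% yearly placebo rate. Assumptions: s², 1:1 allocation, and accrual of 2.5 years for N = 5750 (1.5 years for N = 4126).

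Worked case, s² = 0.3 and N = 5750: r = 0.971, r² = 0.943, effective events 793.

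- If 0.80 is the fully adjusted hazard ratio, power without the covariates is Φ(√793/2 × 0.2231 − 1.960) = 88.1%, against 89.9% with them.
- If 0.80 is the hazard ratio under the present model, adding them is worth 841/0.943 = 892 events, and power is Φ(√892/2 × 0.2231 − 1.960) = 91.5%, against 89.9% as planned.

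| s² (assumed) | HR per SD of residual predictor | Loss, N = 5750 | Effective events | Power without them, if fully adjusted HR is 0.80 | Power with them, if present-model HR is 0.80 | Loss, N = 4126 |
|---|---|---|---|---|---|---|
| 0.1 | 1.37 | 1.8% | 825 | 89.4% | 90.4% | 2.3% |
| 0.2 | 1.56 | 3.7% | 809 | 88.8% | 91.0% | 4.7% |
| 0.3 | 1.73 | 5.7% | 793 | 88.1% | 91.5% | 7.0% |
| 0.5 | 2.03 | 9.6% | 760 | 86.8% | 92.6% | 11.8% |
| 0.8 | 2.45 | 15.3% | 712 | 84.5% | 94.0% | 18.7% |

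The accrual assumption matters little: with 1.5 years at N = 5750, the same formula gives losses of 1.7% to 14.6%.

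**3. Cross-check by simulation**

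200 trials per setting at N = 5750 compared Cox models with treatment alone and with treatment plus the three covariates, so the assumed effects should be read as residual effects. Further assumptions: recent HHF in 25%, atrial fibrillation in 50%, latent correlation 0.3 between NT-proBNP and each of the other two.

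| HR: NT-proBNP per SD / HHF / AF | Variance of predictor | Loss |
|---|---|---|
| 1.3 / 1.3 / 1.1 | 0.10 | 2.4% |
| 1.5 / 1.6 / 1.2 | 0.27 | 3.5% |
| 1.7 / 2.0 / 1.3 | 0.49 | 8.1% |
| 2.0 / 2.5 / 1.4 | 0.80 | 15.7% |

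The two methods agree in order of magnitude.

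**The case against.** The strongest reply is that nothing here is defective. The primary model is fully prespecified, contains the stratification factors and other baseline covariates, and keeps its type I error. Its covariate set is essentially that of the February 2017 SAP. The three-covariate model is not among the 2017 sensitivity analyses; the history table records additional ones in the January 2020 revision. Keeping the original confirmatory model and testing it against a richer one is a defensible order. All of this stands, and it is why the point is an improvement only.

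A reader might infer that the trial is underpowered, or that a known share of its events is wasted. The documents support neither. The power statement does not rely on these covariates, and the powers below 89.9% in the table arise only if 0.80 is taken as the effect conditional on them, which the SAP does not say. Every percentage rests on an assumed prognostic strength. The upper end needs a hazard about 2.4-fold higher per SD of what remains after age, eGFR, LVEF, diabetes, region and sex are in the model. Overlap is likely: Table 6.4: 1 takes the NT-proBNP median separately by atrial fibrillation status, and overlap with age and eGFR is to be expected.

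The change is also not confined to one line. The joint frailty model in 7.5.1 takes over the primary covariates; three more in each of its two submodels add six parameters to a model that already has convergence steps and a fallback. The subgroup, Fine-Gray and other time-to-event models inherit the set too. This stands, but is met by limiting the change to the primary Cox model.

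Finally, the SAP gives no date for the interim analysis, so whether the change can still be made blind cannot be checked from it.

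**Conclusion.** The point holds as a cheap improvement. Three baseline variables that the SAP labels prognostic are left to a sensitivity analysis without a stated reason, and moving them into the primary model would raise power with type I error unchanged.

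The gain is assumption-dependent: about 2% to 15% of effective events at N = 5750 for residual variances of 0.1 to 0.8, and about 4% to 10% for 0.2 to 0.5, probably toward the lower half of that range because of overlap with covariates already in the model. There is no shortfall against the plan. If 0.80 is the hazard ratio under the present model, the change lifts power from 89.9% to about 90.4–94.0%. It is legitimate only if no unblinded look has taken place.

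**What to change.** Provided no unblinded look has taken place:

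1. In 7.4.1, add log(NT-proBNP), baseline atrial fibrillation/flutter and HHF in the last 12 months to the primary Cox model. In 7.4.2, list the present model as the sensitivity analysis.
2. Use the same model at the interim and the final analysis.
3. State which atrial fibrillation definition applies, baseline ECG or history.
4. State that the joint frailty, subgroup, Fine-Gray and other time-to-event models keep the present covariate set unless changed explicitly.

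If unblinding has occurred, leave the primary model as it is; a sentence on why the three covariates stay in the sensitivity analysis would then be enough.

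Cost: SAP wording, and perhaps matching protocol text, since the SAP is based on the protocol's statistical section. Both models are already specified, and no extra patients or visits are needed. The downsides are that the hazard ratio becomes conditional on more covariates, and that the model would differ from that of the parallel trial unless the two plans are aligned.

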7.4.3 Proportional hazards assumption violated

The proportional hazards assumption will be explored by plotting log (-log (survival function)) against the log of time by treatment group and checked for parallelism. The interaction of treatment with log of time will be included in the model described above for an exploratory analysis. Further, Schoenfeld residuals for each covariate and treatment will be plotted against time and log (time).

In case the proportionality assumption is violated for treatment, an attempt will be undertaken to identify groups of patients for which the proportionality assumption holds and a stratified Cox regression will be performed. The HR and corresponding CIs will be obtained from the stratified Cox model.

In addition a piecewise Cox model assuming proportional hazards in a series of consecutive time intervals as proposed by Collett ([6](#)) will be investigated.

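### SAP 7.4.3 answers non-proportional hazards for treatment with a data-driven stratified Cox model, which generally does not remedy a treatment effect that changes over time

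*SAP*

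**What the plan says.** Section 7.4.3 examines proportional hazards (PH) with log-log survival plots by treatment group, an exploratory treatment-by-log(time) term, and Schoenfeld residual plots. No criterion states when PH counts as violated.

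The response is triggered by a violation for treatment specifically: "an attempt will be undertaken to identify groups of patients for which the proportionality assumption holds and a stratified Cox regression will be performed". The section then adds: "The HR and corresponding CIs will be obtained from the stratified Cox model". It names no candidate grouping variables, no selection rule and no limit on attempts. A piecewise Cox model is to be investigated as well, without stated cut-points. The 2017 version of the SAP has the same text.

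Section 7.4.1 defines the primary analysis as a Cox model adjusted for region, diabetes status, age, sex, LVEF and eGFR, and rules out stratification there: "Since the stratification factors are included in the model as covariates, no stratified Cox regression will be used". Section 7.4.3 does not say how its stratified HR relates to that result.

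**The concern.** A stratified Cox model lets each stratum have its own baseline hazard and keeps a single treatment coefficient that is constant over time. It is the usual answer to a covariate that violates PH. Here the trigger is a treatment effect that violates PH, so the response generally repeats the assumption that has just failed.

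The grouping is also open-ended. PH for treatment cannot be judged, nor groups found in which it holds, without treatment codes. The SAP does not use the word unblinded, but that is what the step requires. With no list, rule or limit, two analysts could reach different strata and different HRs from the same data.

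At stake is the clarity of the primary result in the one situation where a single HR is hardest to read: a second HR and CI for the primary endpoint, of undefined status and from a selected model.

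**Working it through.** **Design inputs (SAP 9.6).**
- Power: "The trial is designed to achieve a power of 90% for a two-sided test", at alpha 0.05 and HR 0.80.
- Events: "To achieve this at least 841 patients with a primary event are required".
- Placebo rate: "A 10% yearly event rate in the placebo group is assumed".
- Size and duration: "Assuming an accrual period of 18 months and a follow-up period of 20 months, it was planned to randomise 4126 patients".
- Losses: "The drop-out rate from the trial is assumed to be very low" (below 1% per year, ignored in sizing).

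**Reproducing the plan's figures (1:1 allocation assumed).**
- Events = 4(z₀.₉₇₅ + z₀.₉₀)² / (ln 0.80)² = 4(1.960 + 1.282)² / 0.0498, which gives 845 against the stated 841, a difference under 1%.
- Power with 841 events: Φ(√841/2 × 0.2231 − 1.960) = Φ(1.276) = 89.9%.
- Spending at 60% information with γ = −8: 0.025(1 − e^4.8)/(1 − e^8) = 0.00101. The final one-sided level is 0.0248 and power with the interim is 89.9%, against the stated 0.001, 0.0248 and 89.98%.

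The design reproduces. Section 7.4.3 has no figure of its own, so its remedy was checked by simulation.

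**Why stratification does not generally help.** The stratified hazard is h(t | stratum s, treatment x) = h₀ₛ(t)·exp(βx). Only h₀ₛ varies by stratum; β does not depend on t. If the true effect is β(t), the model still returns one average.

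**Simulation set-up.** N = 4126; follow-up uniform between 20 and 38 months; central hazard −ln(0.9) = 0.105 per year; five equally likely strata; 400 runs per scenario. Each run fits a Cox model with treatment only, then the same model stratified on the true strata, and tests PH against log(time). Baseline hazard multipliers are 0.2, 0.5, 1, 1.5, 2 (10-fold range) or 0.02, 0.1, 0.5, 2, 10 (500-fold). The effect patterns and multipliers are assumptions; the SAP gives none.

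| True treatment effect | Strata range | HR unstratified | HR stratified | PH rejected, unstratified | PH rejected, stratified |
|---|---|---|---|---|---|
| 0.65 in year 1, then 1.00 | 10-fold | 0.847 | 0.836 | 63% | 61% |
| 0.65 in year 1, then 1.00 | 500-fold | 0.894 | 0.783 | 93% | 73% |
| Constant 0.80 within strata | 10-fold | 0.805 | 0.796 | 5% | 6% |
| Constant 0.80 within strata | 500-fold | 0.878 | 0.797 | 19% | 5% |

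The Monte Carlo standard error on 63% is √(0.63 × 0.37/400) = 2.4 points.

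Reading the table:
- With a genuinely waning effect, stratifying on the correct strata leaves most of the non-proportionality in place. Fitting the two periods separately recovers 0.64 and 1.00.
- With a constant effect and extreme heterogeneity, stratification does restore PH. With a 10-fold range there is nothing to restore.

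**Selection.** Under no effect, taking the most extreme of 20 noisy binary stratifiers raised two-sided rejection from 4.7% to 9.0% (600 runs). The 20 candidates and the worst-case pick are assumptions. The figure matters only if the selected model is used for inference.

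**The case against.** The strongest reply is that the primary result is not touched. A reader might infer that the headline HR and the confirmatory test would come from the data-selected model. The documents do not support that. Nothing in the estimand (7.4) or in the primary analysis and testing hierarchy (7.4.1) depends on a PH check, and 7.4.1 excludes stratification. Where this SAP intends a substitute confirmatory analysis it says so, as in 7.5.1 for recurrent HHF if the joint frailty model fails to converge. Section 7.4.3 has no such wording. This reply stands; what remains is that 7.4.3 is silent on whether its HR replaces or supplements the primary one.

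A reader might also infer that a changing treatment effect would go undescribed. That is not so either: the log(time) interaction and the piecewise Cox model in the same section address it directly. The remaining gap is that the piecewise cut-points are not fixed.

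Stratification can also cure non-proportionality that is only apparent and due to omitted baseline heterogeneity. This is true, but in the simulation it took a 500-fold range in a model with no covariates. The 7.4.1 model already adjusts for six baseline factors, which leaves less to omit.

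Finally, the waning scenarios contain no group in which PH holds, so the SAP's search would find none. That is fair. It also shows a gap, because the section gives no instruction for that outcome, which is what a general waning effect would produce.

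**Conclusion.** The point holds as a flaw in a conditional rule. The remedy in 7.4.3 does not generally match its trigger, the group search is unspecified and needs treatment codes, and the status of the resulting HR is undefined. The structural argument follows from the form of the model and does not rest on the simulation.

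The numerical consequence for the HR is small with moderate strata (0.847 against 0.836) and larger only under extreme ones (0.894 against 0.783). In both waning scenarios non-proportionality largely remains after stratification (61% and 73% of runs). These figures rest on an assumed waning pattern and on strata known without error.

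Inflation of the type I error should not be inferred. The move from 4.7% to 9.0% needs a worst-case pick among 20 assumed candidates and use of that model for testing, and the SAP states no such use. The rule should be corrected, but it does not undermine the primary test as specified in 7.4.1.

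**What to change.** In section 7.4.3:
1. Delete the search for groups and the HR and CIs from the stratified Cox model.
2. State that the Cox HR and test of 7.4.1 remain the primary result whatever the PH diagnostics show.
3. Make the already planned piecewise Cox model the supplementary description when non-proportionality is seen, with a stated criterion for that judgement and cut-points fixed before unblinding, for example at 12 and 24 months. Check the later cut-point against blinded follow-up first, because 9.6 allows recruitment to continue until 6 months before the event target is expected.

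A difference in restricted mean event-free time to a horizon set in advance is an optional addition.

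The cost is a change of SAP wording and at most one more table. What is given up is the rare case in which stratification would have removed apparent non-proportionality caused by very large baseline heterogeneity.
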